**Table 4-2 Imputation of partial end dates (AE, CM)**

Missing Element	Rule (*= $\min$ (last study treatment date plus 30 days, death date, cut-off date, withdrawal of consent date))
day, month, and year	

No imputation will be done for completely missing dates

day, month	

If partial end date contains year only, set end date = earliest of 31DecYYYY or end date of the on-treatment period *

day	

If partial end date contains month and year, set end date = earliest of last day of the month or end date of the on-treatment period*

Any AEs and ConMeds with partial/missing dates will be displayed as such in the data listings.

Any AEs and ConMeds which are continuing as per data cut-off will be shown as 'ongoing' rather than the end date provided.

The above imputations are only used for analyses of time to and duration of AEs and concomitant medications. For completely missing end date, it will not be considered as an event date for duration of AE analysis.

The above rules will be used for imputation of AE end dates if AE start date is before last dose of study treatment. In this study, SAEs suspected to be related with study treatment or ET alone after EOT will continue to be collected. The imputation of end date of SAE during the post-treatment period will be based on the same rules by replacing end date of on-treatment period in above table with last contact date.

#### 4.1.2.1 Other imputations

Not applicable

## 4.2 AEs coding/grading

Adverse events are coded using the Medical dictionary for regulatory activities (MedDRA) terminology.

The latest available MedDRA version at the time of the analyses will be used. The MedDRA version used will be specified in the footnote of relevant tables.

AEs will be assessed according to the Common Terminology Criteria for Adverse Events (CTCAE) version 4.03.

The CTCAE represents a comprehensive grading system for reporting the acute and late effects of cancer treatments. CTCAE grading is by definition a 5-point scale generally corresponding to mild, moderate, severe, life threatening, and death. This grading system inherently places a value on the importance of an event, although there is not necessarily proportionality among grades (a grade 2 is not necessarily twice as bad as a grade 1).

### **4.3 Laboratory parameters derivations**

Grade categorization of lab values will be assigned programmatically as per NCI Common Terminology Criteria for Adverse Events (CTCAE) version 4.03. The calculation of CTCAE grades will be based on the observed laboratory values only, clinical assessments will not be taken into account. The criteria to assign CTCAE grades are given in Novartis internal criteria for CTCAE grading of laboratory parameters. The latest available version of the document based on the underlying CTCAE version 4.03 at the time of analysis will be used. For laboratory tests where grades are not defined by CTCAE version 4.03, results will be graded by the low/normal/high classifications based on laboratory normal ranges.

A severity grade of 0 will be assigned for all non-missing lab values not graded as 1 or higher. Grade 5 will not be used. For laboratory tests that are graded for both low and high values, summaries will be done separately and labelled by direction, e.g., sodium will be summarized as hyponatremia and hypernatremia.

CTC grades for laboratory values in Novartis Oncology (based on CTCAE v4.03 – June 2010)

Page 1

Lab test (toxicity)	SI unit	Lab test (NCDS)	Normal ranges (Merck manual, July 2015) and conversion factors	CTC Grades 				
				0	1	2	3	4
Hematology								
WBC ↓ WBC  (Leukocytosis)	10  /L 10  /L	WBC WBC	3.9 – 10.7 x 10  /L	≥ LLN	< LLN - 3.0 x 10  /L -	< 3.0 – 2.0 x 10  /L -	< 2.0 – 1.0 x 10  /L > 100 x 10  /L	< 1.0 x 10  /L -
Hemoglobin  (Anemia)	g/L	HGB	120 - 160 g/L or 7.4 - 9.9 mmol/L (F) 140 - 170 g/L or 8.7 – 10.6 mmol/L (M) (16.113 x mmol/L = g/L)	≥ LLN	< LLN - 100 g/L < LLN - 6.2 mmol/L Increase >0-20 g/L above ULN	< 100 - 80 g/L < 6.2 - 4.9 mmol/L Increase >20-40 g/L above ULN	< 80 g/L < 4.9 mmol/L Increase >40 g/L above ULN	-
Hemoglobin ↑	g/L	HGB						
Platelets ↓	10  /L	PLAT	150 - 350 x 10  /L	≥ LLN	< LLN - 75.0 x 10  /L	< 75.0 - 50.0 x 10  /L	< 50.0 - 25.0 x 10  /L	< 25.0 x 10  /L
Neutrophils  ↓	10  /L	NEUT		≥ 2x10  /L	< 2.0 - 1.5 x 10  /L	< 1.5 - 1.0 x 10  /L	< 1.0 - 0.5 x 10  /L	< 0.5 x 10  /L
Lymphocytes  ↓	10  /L	LYM		≥ 1.5x10  /L	< 1.5 - 0.8 x 10  /L	< 0.8 - 0.5 x 10  /L	< 0.5 - 0.2 x 10  /L	< 0.2 x 10  /L
Lymphocytes ↑	10  /L	LYM			-	> 4 - 20 x 10  /L	> 20 x 10  /L	-
Biochemistry								
AST ↑	U/L	AST	0 - 35 U/L or 0 – 0.58 ukat/L (60 x ukat/L = U/L)	≤ ULN	> ULN - 3.0 x ULN	> 3.0 - 5.0 x ULN	> 5.0 - 20.0 x ULN	> 20.0 x ULN
ALT ↑	U/L	ALT	0 - 35 U/L or 0 – 0.58 ukat/L (60 x ukat/L = U/L)	≤ ULN	> ULN - 3.0 x ULN	> 3.0 - 5.0 x ULN	> 5.0 - 20.0 x ULN	> 20.0 x ULN
Total bilirubin ↑	umol/L	BILI	5.1 – 20.5 umol/L or 0.3 – 1.2 mg/dL (17.1 x mg/dL = umol/L)	≤ ULN	> ULN - 1.5 x ULN	> 1.5 - 3.0 x ULN	> 3.0 - 10.0 x ULN	> 10.0 x ULN
Alk. Phosphatase ↑	U/L	ALP	36 - 92 U/L or 0.5 - 1.5 ukat/L (60 x ukat/L = U/L)	≤ ULN	> ULN - 2.5 x ULN	> 2.5 - 5.0 x ULN	> 5.0 - 20.0 x ULN	> 20.0 x ULN
Creatinine  ↑	umol/L	CREAT	61.9 - 115 umol/L or 0.7 – 1.3 mg/dL (88.4 x mg/dL = umol/L)	≤ ULN	> ULN - 1.5 x ULN	> 1.5 - 3.0 x ULN	> 3.0 - 6.0 x ULN	> 6.0 x ULN
Creatinine kinase  ↑	U/L	CK	30 - 170 U/L or 0.5 – 2.83 ukat/L (60 x ukat/L = U/L)	≤ ULN	> ULN - 2.5 x ULN	> 2.5 - 5.0 x ULN	> 5.0 - 10.0 x ULN	> 10.0 x ULN
Albumin  (Hypoalbuminemia)	g/L	ALB	35 - 55 g/L or 3.5 to 5.5 g/dL	≥ LLN	< LLN - 30 g/L	< 30 - 20 g/L	< 20 g/L	-
Total Cholesterol ↑	mmol/L	CHOL	3.88 – 5.15 mmol/L or 150 - 199 mg/dL (38.67 x mg/dL = mmol/L)	≤ ULN	> ULN - 7.75 mmol/L > ULN - 300 mg/dL	> 7.75 - 10.34 mmol/L > 300 – 400 mg/dL	> 10.34-12.92 mmol/L > 400 – 500 mg/dL	> 12.92 mmol/L > 500 mg/dL
Lipase ↑	U/L	LIPASE	<95 U/L or <1.58 ukat/L (60 x ukat/L = U/L)	≤ ULN	> ULN - 1.5 x ULN	> 1.5 - 2.0 x ULN	> 2.0 - 5.0 x ULN	> 5.0 x ULN
Amylase ↑	U/L	AMYLASE	0 - 130 U/L or 0 – 2.17 ukat/L (60 x ukat/L = U/L)	≤ ULN	> ULN - 1.5 x ULN	> 1.5 - 2.0 x ULN	> 2.0 - 5.0 x ULN	> 5.0 x ULN
Uric acid  (Hyperuricemia)	umol/L	URATE	150 - 470 umol/L or 2.5 – 8 mg/dL (59.48 x mg/dL = umol/L)	≤ ULN	> ULN – 10 mg/dL > ULN – 595 umol/L	-	-	> 10 mg/dL > 595 umol/L

ULN = Upper Limit of Normal range; LLN = Lower Limit of Normal range

LAB - CTC grades in Novartis Oncology (26Oct15)

CTC grades for laboratory values in Novartis Oncology (based on CTCAE v4.03 – June 2010)

Page 2

Lab test (toxicity)	SI unit	Lab test (NCDS)	Normal ranges (Merck manual, July 2015) and conversion factors	CTC Grades 				
				0	1	2	3	4
Phosphorus  (Hypophosphatemia)	mmol/L	PHOS	0.97 – 1.45 mmol/L or 3.0 – 4.5 mg/dL (0.32 x mg/dL = mmol/L)	≥ LLN	< LLN - 2.5 mg/dL < LLN - 0.8 mmol/L	< 2.5 - 2.0 mg/dL < 0.8 - 0.6 mmol/L	< 2.0 - 1.0 mg/dL < 0.6 - 0.3 mmol/L	< 1.0 mg/dL < 0.3 mmol/L
Calcium (corrected)  (Hypercalcaemia)	mmol/L	CACALC	2.2 - 2.6 mmol/L or 9 - 10.5 mg/dL (0.2495 x mg/dL = mmol/L)	≤ ULN	> ULN - 11.5 mg/dL > ULN - 2.9 mmol/L	> 11.5 - 12.5 mg/dL > 2.9 - 3.1 mmol/L	> 12.5 - 13.5 mg/dL > 3.1 - 3.4 mmol/L	> 13.5 mg/dL > 3.4 mmol/L
Calcium (corrected)  (Hypocalcaemia)	mmol/L	CACALC		≥ LLN	< LLN - 8.0 mg/dL < LLN - 2.0 mmol/L	< 8.0 - 7.0 mg/dL < 2.0 - 1.75 mmol/L	< 7.0 - 6.0 mg/dL < 1.75 - 1.5 mmol/L	< 6.0 mg/dL < 1.5 mmol/L
Magnesium  (Hypermagnesaemia)	mmol/L	MG	0.62 – 0.99 mmol/L or 1.5 – 2.4 mg/dL (0.4114 x mg/dL = mmol/L)	≤ ULN	> ULN - 3.0 mg/dL > ULN - 1.23 mmol/L	-	> 3.0 - 8.0 mg/dL > 1.23 - 3.3 mmol/L	> 8.0 mg/dL > 3.3 mmol/L
Magnesium  (Hypomagnesaemia)	mmol/L	MG		≥ LLN	< LLN - 1.2 mg/dL < LLN - 0.5 mmol/L	< 1.2 - 0.9 mg/dL < 0.5 - 0.4 mmol/L	< 0.9 - 0.7 mg/dL < 0.4 - 0.3 mmol/L	< 0.7 mg/dL < 0.3 mmol/L
Glucose (non-fasting)  (Hyperglycaemia)	mmol/L	GLUCSN	<7.8 mmol/L or <140 mg/dL (0.05551 x mg/dL = mmol/L)	≤ ULN	-	> ULN - 250 mg/dL > ULN - 13.9 mmol/L	> 250 - 500 mg/dL > 13.9 - 27.8 mmol/L	> 500 mg/dL > 27.8 mmol/L
Glucose (fasting)  (Hyperglycaemia)	mmol/L	GLUCSF	3.9 – 5.8 mmol/L or 70 - 105 mg/dL (0.05551 x mg/dL = mmol/L)	≤ ULN	> ULN - 160 mg/dL > ULN - 8.9 mmol/L	> 160 - 250 mg/dL > 8.9 - 13.9 mmol/L	> 250 - 500 mg/dL > 13.9 - 27.8 mmol/L	> 500 mg/dL > 27.8 mmol/L
Glucose  (Hypoglycaemia)	mmol/L	GLUCSN/ GLUCSF		≥ LLN	< LLN - 55 mg/dL < LLN - 3.0 mmol/L	< 55 - 40 mg/dL < 3.0 - 2.2 mmol/L	< 40 - 30 mg/dL < 2.2 - 1.7 mmol/L	< 30 mg/dL < 1.7 mmol/L
Potassium  (Hyperkaemia)	mmol/L	K	3.5 - 5.0 mmol/L (0.2558 x mg/dL = mEq/L = mmol/L)	≤ ULN	> ULN - 5.5 mmol/L	> 5.5 - 6.0 mmol/L	> 6.0 - 7.0 mmol/L	> 7.0 mmol/L
Potassium  (Hypokaemia)	mmol/L	K		≥ LLN	< LLN - 3.0 mmol/L	-	< 3.0 - 2.5 mmol/L	< 2.5 mmol/L
Sodium  (Hyponatremia)	mmol/L	SODIUM	136 - 145 mmol/L (0.435 x mg/dL = mEq/L = mmol/L)	≤ ULN	> ULN - 150 mmol/L	> 150 - 155 mmol/L	> 155 - 160 mmol/L	> 160 mmol/L
Sodium  (Hyponatremia)	mmol/L	SODIUM		≥ LLN	< LLN - 130 mmol/L	-	< 130 - 120 mmol/L	< 120 mmol/L
Triglyceride (2) †	mmol/L	TRIG	< 2.82 mmol/L or < 250 mg/dL (0.01129 x mg/dL = umol/L)	< 150 < 1.71	≥ 150 - 300 mg/dL ≥ 1.71 - 3.42 mmol/L	> 300 - 500 mg/dL > 3.42 - 5.7 mmol/L	> 500 - 1000 mg/dL > 5.7 - 11.4 mmol/L	> 1000 mg/dL > 11.4 mmol/L
Coagulation								
INR (2) †	1	INR	0.8 – 1.2	≤ ULN	> ULN - 1.5 x ULN	> 1.5 - 2.5 x ULN	> 2.5 x ULN	-
Activated partial thromboplastin time (2) †	sec	APTT	25 - 35 sec	≤ ULN	> ULN - 1.5 x ULN	> 1.5 - 2.5 x ULN	> 2.5 x ULN	-
Fibrinogen 	g/L	FIBRINO	1.5 – 3.5 g/L or 150 – 350 mg/dL (0.01 x mg/dL = g/L)	≥ LLN	< LLN - 0.75 x LLN	< 0.75 - 0.5 x LLN	< 0.5 - 0.25 x LLN	< 0.25 x LLN

ULN = Upper Limit of Normal range; LLN = Lower Limit of Normal range

(1) = LAB CTC grades 1, 2, 3, 4 overrule the study specific (central or local) normal range criteria, e.g. if ULN of Sodium is 151 mmol/L and the value is 151 mmol/L, CTC grade 2 is assigned although the value is ≤ ULN.

(2) = Life-threatening consequences and/or hospitalization are not considered for determination of LAB CTC grades 3 and 4. Concomitant usage of anticoagulation therapy (for INR and Fibrinogen) is not considered either.

(3) = Values and LNRs for blood differentials can be given as %, absolute values should then be calculated using WBC. Generally, ≥ 1.5 x 10^9/L (lymphocytes) and ≥ 2 x 10^9/L (neutrophils) are considered as LAB CTC grade 0

(4) = For Creatinine and Fibrinogen, the comparison with baseline is not considered for derivation of LAB CTC grades

LAB - CTC grades in Novartis Oncology (26Oct15)

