**Document History – Changes compared to previous final version of SAP**

Date	Time Point	Reasons for update	Outocme for update	Section and title impacted (Current)
31-May-2017	Before DBL	First Version		
01-May-2019	Before DBL	The trial had an early enrollment closure on 12 February 2018; the protocol was amended on April 2018.	The study is now a Phase II trial. All sections related to Efficacy analysis has been removed.  Efficacy data will be summarized by a listing only.	All the sections of the earlier version has been impacted
23-Feb-2020	Before DBL	
 
1. Add one lab param for the shift table.
 
2. Clarify which CRS version will be used.
 
3. For exposure data, GnRH agonist will be combined with ET to report.
 
	
 
1. Blood Creatinine was added to report.
 
2. Added a sentence to use the most up-to-date CRS.
 
3. For exposure data, GnRH was combined with ET to report.
 
	
 
1. Section 4.3
 
2. section 2.7.1.1
 
3. section 2.4.1
 

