#### **2.7.3      Laboratory data**

On analyzing laboratory data, data from all sources (central and local laboratories) will be combined. The summaries will include all assessments available for the lab parameter collected no later than 30 days after the last study treatment administration date (see Section 2.1.1).

Grading of laboratory values will be assigned programmatically as per National Cancer Institute CTCAE version 4.03. The calculation of CTCAE grades will be based on the observed laboratory values only, clinical assessments will not be taken into account.

CTCAE Grade 0 will be assigned for all non-missing values not graded as 1 or higher. Grade 5 will not be used.

For laboratory tests where grades are not defined by CTCAE, results will be categorized as low/normal/high based on laboratory normal ranges.

For hematology: Absolute neutrophils, Absolute granulocytes, Hemoglobin, WBC, Platelet counts, PTT.

For Biochemistry: Albumin, Alkaline phosphatase, **Blood Creatinine**, SGPT (ALT), Amylase, SGOT (AST, Total bilirubin, Calcium (hyper & hypo), GGT, Glucose (hyper & hypo), Lipase, Magnesium (hyper & hypo), Phosphate, Potassium (hyper & hypo), Sodium (hyper & hypo).

For both groups of laboratory tests, shift tables to compare baseline to the worst postbaseline value will be produced using CTCAE grade and normal range.

A single listing for all the laboratory parameters with grades, normal ranges and lab values flagged to indicate that the values are outside the normal range will be reported.

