## Imputation Rules

CTC grading for blood differentials is based on absolute values. However, this data may not be reported as absolute counts but rather as percentage of WBC.

If laboratory values are provided as '<X' (i.e. below limit of detection) or '>X', prior to conversion of laboratory values to SI unit, these numeric values are set to X.

The following rules will be applied to derive the WBC differential counts when only percentages are available for a xxx differential

$$\text{xxx count} = (\text{WBC count}) * (\text{xxx \%value} / 100)$$

Further derivation of laboratory parameters might be required for CTCAE grading. For instance, corrected calcium can be derived using the reported total calcium value and albumin at the same assessment using the following formula:

$$\text{Corrected Calcium (mg/dL)} = \text{Calcium (mg/dL)} - 0.8 [\text{Albumin (g/dL)} - 4]$$

In order to apply the above formula, albumin values in g/L will be converted to g/dL by multiplying by 0.1), calcium values in mmol/L will be converted to mg/dL by dividing by 0.2495. For calculation of laboratory CTC grades 0 and 1, the normal range for derived corrected calcium is set to the same limits (in mg/dL) as for calcium.

CTC grades for the derived absolute WBC differential counts (neutrophils, lymphocytes) and corrected calcium will be assigned as described above for grading.

Estimated glomerular filtration rate (eGFR) will be calculated using Cockcroft-Gault formula:

$$eGFR = \frac{(140 - Age) \times Mass(in\ kilograms) \times [0.85\ if\ Female]}{72 \times Serum\ Creatinine\ (in\ mg/dL)}$$

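### The only tabulated renal laboratory measure is a creatinine shift graded against the ULN, which can understate within-patient change, and the eGFR that the SAP defines feeds no summary

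*SAP*

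**What the plan says.** Under SAP section 2.7.3, "shift tables to compare baseline to the worst postbaseline value will be produced using CTCAE grade and normal range". "Blood Creatinine" is the only renal parameter in that section's list of tests, and eGFR is not in it. Section 2.7.3 also fixes that "CTCAE Grade 0 will be assigned for all non-missing values not graded as 1 or higher", and on the basis of grading it says: "The calculation of CTCAE grades will be based on the observed laboratory values only, clinical assessments will not be taken into account".

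The grading table in section 4.3 gives creatinine as grade 0 at or below the ULN, grade 1 up to 1.5 times, grade 2 up to 3 times, grade 3 up to 6 times and grade 4 above that, all as multiples of the ULN. Footnote (4) to the table reads: "For Creatinine and Fibrinogen, the comparison with baseline is not considered for derivation of LAB CTC grades". Under Imputation Rules in the same section, "Estimated glomerular filtration rate (eGFR) will be calculated using Cockcroft-Gault formula". No table, category or threshold in the SAP takes up that value.

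The Document History records for February 2020 that "Blood Creatinine was added to report". Renal impairment is one of the AESI groupings in Table 2-5, and section 2.7.1.1 builds all AESIs from adverse events alone.

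**The concern.** Frequency and severity of laboratory abnormalities belong to the primary endpoint (Table 1-1 and section 2.4.2), and renal impairment is a named safety topic. The one table that counts laboratory renal change by arm uses a scale on which a patient's own starting value plays no part in the grade. A patient who starts low in the normal range can lose a good deal of estimated renal function before the grade moves, and more again before it reaches grade 2 or 3.

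The other routes do not supply the missing count. The laboratory listing prints every value but flags only those outside the normal range. The renal AESI needs an event to have been reported. An eGFR summary would show the change directly, but the SAP derives the quantity and then gives it no output.

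The SAP does use within-patient change elsewhere: section 2.7.4.1 has change-from-baseline categories for ECG, and Table 2-6 has them for most vital signs.

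**Working it through.** The SAP states no figure for this point, so there is none to reproduce. The inputs come from section 4.3:

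- printed creatinine range 61.9 to 115 umol/L, or 0.7 to 1.3 mg/dL, with factor 88.4
- grade limits at 1, 1.5, 3 and 6 times the ULN
- the Cockcroft-Gault formula, (140 − age) × weight × 0.85 (if female) / (72 × creatinine in mg/dL)

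**Unit check.** 0.7 × 88.4 = 61.88 and 1.3 × 88.4 = 114.92, which agree with the printed limits.

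**Largest rise still grade 0.** This is ULN / baseline. At fixed age and weight the formula is inversely proportional to creatinine, so the matching fall in eGFR is 1 − baseline / ULN.

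| Baseline (mg/dL) | Largest rise shown as 0 to 0 | Fall in eGFR |
|---|---|---|
| 0.7 | 1.3 / 0.7 = 1.86 | 46% |
| 0.8 | 1.3 / 0.8 = 1.63 | 38% |
| 0.9 | 1.3 / 0.9 = 1.44 | 31% |
| 1.0 | 1.3 / 1.0 = 1.30 | 23% |

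In each row both values lie within the normal range, so the normal-range shift shows no movement either.

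**Absolute example (assumed patient: woman, 60 years, 70 kg).** The numerator is 80 × 70 × 0.85 = 4760. At 61.9 umol/L (0.700 mg/dL) the result is 4760 / (72 × 0.700) = 94 mL/min. At 115 umol/L (1.301 mg/dL) it is 4760 / (72 × 1.301) = 51 mL/min.

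**Above the range.** From 61.9 umol/L, grade 1 runs to 1.5 × 115 = 172.5 umol/L, which is 172.5 / 61.9 = 2.79 times baseline. Grade 3 starts only above 3 × 115 = 345 umol/L, which is 345 / 61.9 = 5.57 times baseline. The compression is therefore not confined to values within the range.

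**Sensitivity to the ULN.** With an assumed local ULN of 90 umol/L and the same baseline, the largest rise still grade 0 is 90 / 61.9 = 1.45, a fall in eGFR of 1 − 61.9 / 90 = 31%. Grade 2 then needs more than 135 / 61.9 = 2.18 times baseline.

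**What an own-baseline count would add.** With the printed range, a category above 1.5 times baseline picks up within-range rises only for baselines below 1.3 / 1.5 = 0.87 mg/dL. With a ULN of 90 and a baseline of 61.9 it picks up none, because 1.45 is below 1.5. An eGFR summary would still reflect that 31% fall.

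**The case against.** The strongest reply is that nothing here is wrong. The rule is stated in a footnote to a dated sponsor-wide grading table, is reproducible, and is applied alike to both arms. Every laboratory test in section 2.7.3 gets the same kind of shift table, and any range-based shift hides movement within the range. That stands: this is an analysis choice, and the proposal is an addition to it.

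The 1.86 figure needs a baseline at the lower limit and a worst value at the upper limit. The printed range is a reference range, while footnote (1) of the table speaks of study-specific central or local ranges. That stands too, which is why a span of results is given. The SAP does not show how many patients start low enough for this to matter.

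Three stronger readings are tempting, and the document supports none of them:

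- A reader might infer that near-doublings of creatinine would go unreported. The values stay in the listing, and an event may be reported as an adverse event. What is missing is a laboratory-based count by arm.
- A reader might infer that the table was added to show a renal effect and then defeats its purpose. The Document History records only the addition, with no reason.
- A reader might infer that the grading is a mistake because section 2.7.3 mentions only clinical assessments as set aside. The footnote discloses the omission, so the main text is incomplete on this point but does not contradict it.

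A last objection is that worst-value counts by arm depend on follow-up. Under section 1.1 placebo was stopped permanently, while ribociclib patients could continue. This is true, but it affects the planned worst-value shift table in the same way, and a footnote deals with it.

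**Conclusion.** The point holds as a cheap improvement, not as the correction of an error. The only tabulated laboratory measure of renal change is graded against the ULN with the baseline comparison set aside, and the derived eGFR has no use in any summary. For patients with low-normal baseline creatinine, the shift table can understate within-patient change.

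On the printed illustrative range the largest rise shown as no shift runs from 1.30 times (baseline 1.0 mg/dL) to 1.86 times (baseline at the lower limit), or 23% to 46% in eGFR. With an assumed ULN of 90 umol/L it is at most 1.45 times from 61.9 umol/L. These figures assume fixed age and weight, and a worst value exactly at the ULN. They bound what a single patient's entry can hide and do not estimate how often it happens.

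**What to change.** 1. Keep the ULN-based shift table, and state in section 2.7.3 that its creatinine grades omit the baseline comparison.
2. Add the number and percentage of patients by arm whose worst on-treatment creatinine exceeds 1.5 times and 3 times their own baseline. These are two of the multiples that the ULN grades already use.
3. Add a summary by arm of the baseline and lowest on-treatment Cockcroft-Gault value, labelled as creatinine clearance in mL/min. State which weight enters the formula. This gives the derivation in section 4.3 an output and shows falls that the 1.5-times category would miss.
4. Footnote both tables to say that time on treatment differs between arms, because placebo was stopped.

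The cost is two more descriptive tables from data already collected. A creatinine effect may look less favourable than in the shift table alone.

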## Imputation Rules

CTC grading for blood differentials is based on absolute values. However, this data may not be reported as absolute counts but rather as percentage of WBC.

If laboratory values are provided as '<X' (i.e. below limit of detection) or '>X', prior to conversion of laboratory values to SI unit, these numeric values are set to X.

The following rules will be applied to derive the WBC differential counts when only percentages are available for a xxx differential

$$\text{xxx count} = (\text{WBC count}) * (\text{xxx \%value} / 100)$$

Further derivation of laboratory parameters might be required for CTCAE grading. For instance, corrected calcium can be derived using the reported total calcium value and albumin at the same assessment using the following formula:

$$\text{Corrected Calcium (mg/dL)} = \text{Calcium (mg/dL)} - 0.8 [\text{Albumin (g/dL)} - 4]$$

In order to apply the above formula, albumin values in g/L will be converted to g/dL by multiplying by 0.1), calcium values in mmol/L will be converted to mg/dL by dividing by 0.2495. For calculation of laboratory CTC grades 0 and 1, the normal range for derived corrected calcium is set to the same limits (in mg/dL) as for calcium.

CTC grades for the derived absolute WBC differential counts (neutrophils, lymphocytes) and corrected calcium will be assigned as described above for grading.

Estimated glomerular filtration rate (eGFR) will be calculated using Cockcroft-Gault formula:

$$eGFR = \frac{(140 - Age) \times Mass(in\ kilograms) \times [0.85\ if\ Female]}{72 \times Serum\ Creatinine\ (in\ mg/dL)}$$

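### Setting laboratory results reported as <X or >X to X gives the milder CTCAE grade when X is a strict grade limit and the sign points to the severe side

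*SAP*

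**What the plan says.** SAP section 4.3, under Imputation Rules, covers results that a laboratory reports with a < or > sign. Before units are converted, "these numeric values are set to X". No sign or offset is kept for grading.

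Section 2.7.3 states: "Grading of laboratory values will be assigned programmatically as per National Cancer Institute CTCAE version 4.03". Section 4.3 adds: "The calculation of CTCAE grades will be based on the observed laboratory values only, clinical assessments will not be taken into account". The grades feed shift tables from baseline to the worst post-baseline value. Section 2.7.3 also counts patients whose liver values exceed strict multiples of ULN, up to 20 x ULN for ALT or AST.

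In the grading table of section 4.3 the limit nearly always belongs to the milder grade:
- Grade 3 for AST and ALT is "> 5.0 - 20.0 x ULN"; grade 4 starts strictly above 20.0 x ULN.
- Grade 3 for high potassium is "> 6.0 - 7.0 mmol/L"; grade 4 starts strictly above 7.0.
- Grade 3 for low sodium is "< 130 - 120 mmol/L"; grade 4 starts strictly below 120.
- Neutrophils, platelets and WBC follow the same pattern, with grade 4 strictly below 0.5, 25.0 and 1.0 x 10^9/L.

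**The concern.** A < or > sign says on which side of X the true value lies. If X is a grade limit, that sign is the only information that decides the grade, and the rule removes it before grading. None of the four table footnotes puts it back, and neither does any other section of the SAP.

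Laboratory abnormalities are part of the primary endpoint (Table 1-1 and section 2.4.2). A worst-value table depends on extreme results, and those are where a sign tends to appear. Section 2.7.3 combines central and local laboratories, so reporting limits need not be uniform. Neutrophils, WBC, platelets and glucose are all on that section's list of tests for the shift tables.

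**Working it through.** The SAP gives no figure to reproduce on this point. The check applies its rule to its own table.

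**Step 1: X equal to a strict limit, in the unit used for grading, sign towards the severe side.**

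| Reported result | Value used | Grade assigned | Grade implied by the sign |
|---|---|---|---|
| Neutrophils <0.5 | 0.5 | 3 | 4 |
| Neutrophils <1.0 | 1.0 | 2 | at least 3 |
| Platelets <25 | 25 | 3 | 4 |
| WBC <1.0 | 1.0 | 3 | 4 |
| Sodium <120 mmol/L | 120 | 3 | 4 |
| Potassium >7.0 mmol/L | 7.0 | 3 | 4 |
| AST or ALT >20 x ULN | 20 x ULN | 3 | 4 |

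Over the main numeric limits of the table, 90 strict limits were checked (38 in the low direction, 52 in the high direction). Set-to-X gives the milder grade at all 90. The loss is usually one grade. It is larger where the table skips a grade: low potassium has no grade 2, so <3.0 set to 3.0 is grade 1 instead of at least 3.

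**Step 2: X reported in mg/dL at the mg/dL limit, then graded on the rounded SI limit.** The formula is X times the table's conversion factor. This was done for 20 limits of phosphorus, calcium, magnesium and glucose.
- Glucose >500 mg/dL: 500 x 0.05551 = 27.755 mmol/L, which is not above 27.8, so grade 3. On the mg/dL limit 500 is also grade 3. The reported result is grade 4 on the mg/dL limit.
- Low magnesium <1.2 mg/dL: 1.2 x 0.4114 = 0.494 mmol/L, which is below 0.5, so the more severe grade is kept.
- Low calcium <8.0 mg/dL: 8.0 x 0.2495 = 1.996 mmol/L, which is below 2.0, so the more severe grade is kept.

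In all, 11 of the 20 limits give the milder grade and 9 keep the more severe one:

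| Test | Milder | More severe kept |
|---|---|---|
| Phosphorus, low | 3 | 0 |
| Calcium, high | 2 | 1 |
| Calcium, low | 0 | 3 |
| Magnesium, high | 1 | 1 |
| Magnesium, low | 0 | 3 |
| Glucose, high (fasting) | 3 | 0 |
| Glucose, low | 2 | 1 |
| Total | 11 | 9 |

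Which way a limit falls depends on how its SI figure was rounded.

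**Step 3: the other positions of X.**
- X already beyond the grade 4 limit: set-to-X grades correctly.
- X inside a grade band: the true grade is not known, and no error can be shown.
- Sign towards the milder side, such as neutrophils >0.5: X gives grade 3, the worst grade compatible with the result.
- Triglyceride grade 1 is inclusive (from 150 mg/dL), so <150 set to 150 moves from grade 0 up to grade 1. Triglyceride is not on the section 2.7.3 list.

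**Step 4: liver summaries.** These cut-offs are strict. A result of >X with X equal to the stated multiple of ULN is set to that multiple and is not counted as exceeding it.

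**The case against.** Setting a signed result to X is a common convention. Here it is explicit, prespecified and reproducible, and the analysis is purely descriptive. The rule describes <X as a detection limit, and the SAP gives no such limit for any test. Where the limit lies well beyond the grade 4 limit, the grade is right. An affected result also need not change a patient's category, because the shift table uses the worst value and another result may already reach the higher grade. Finally, section 4.3 refers to the latest version of an internal grading document, which may handle signed values and cannot be seen here.

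Most of this stands as a limit on size. It does not remove the fault. A convention suited to means or display is placed in the section that derives grades, and as printed it assigns a grade that the reported result rules out.

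Three stronger readings are tempting, and the SAP does not support them:
- **That special-interest counts are too low.** Neutropenia, leukopenia and thrombocytopenia are named groupings, but section 2.7.1.1 bases all of them on adverse events only, so laboratory grades cannot change them.
- **That the error always runs towards less severe.** The triglyceride limit and signs pointing to the milder side behave otherwise, as step 3 shows.
- **That a percentage-point effect can be stated.** The SAP gives no sample size and no frequency of such results.

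**Conclusion.** The rule is wrong as written, in a narrow case, and the point is minor. If X equals a strict grade limit in the unit used for grading and the sign points to the severe side, a result known to be in the more severe grade gets the milder one. The same holds for the strict liver cut-offs. The outputs at risk are the worst-post-baseline shift tables and the liver summaries. The effect is usually one grade per affected result. How many patients would change category cannot be estimated from the SAP, and the number is probably low. The conclusion assumes that the program follows the printed rule and table, and that at least one contributing laboratory has a reporting limit equal to a grade limit. The SAP shows neither that this occurs nor that it does not.

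**What to change.** Add to section 4.3, under Imputation Rules: *For CTCAE grading and threshold summaries, a directly reported value of <X or >X is treated as strictly below or above X, so that when X equals a limit the grade on the side shown by the sign is assigned. X is compared with the limit printed for the unit in which the result was reported. X is used for numeric display and for derived parameters (differential counts from percentages, corrected calcium), and such derived values are flagged.*

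The sentence on units is needed because glucose >500 mg/dL would otherwise still be graded 3 after conversion to 27.755 mmol/L. Derived values are kept apart because the sign of an input does not carry over simply: albumin enters the corrected-calcium formula with a negative coefficient, so <X for albumin pushes the result upwards. The wording also corrects the triglyceride case.

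The cost is a few lines in the SAP and a matching change in the grading program, which must keep the sign from the source data. No new data are needed.
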